3.2.2 Primary Performance Measure

- MR Reduction to $\leq 2+$ at 30 days and 12 months

3.2.3 Secondary Measures

1. Adverse event assessment (all follow up visits)
2. EQ-5D-5L or KCCQ at baseline, 30 days and 12 months, if available
3. 6MWT at baseline, 30 days, and 12 months, if available
4. NYHA assessment at baseline, 30 days and 12 months, if available

3.3 Number of Planned Patients

All patients treated with the commercially available PASCAL Transcatheter Valve Repair System and who are not part of any ongoing PASCAL pre or post market study, will be asked to participate in this registry. A minimum of 200 patients are expedited to be enrolled in the registry at sites performing transcatheter valve repair where commercialized PASCAL Transcatheter Device is available.

A patient will be considered enrolled in the registry once the patient has signed the ICF and the procedure has begun (defined as PASCAL guide sheath is inserted into the vasculature).

3.4 Number of Planned Registry Sites

A minimum of 10 sites will be activated for the Registry.

3.5 Inclusion Criteria

Patients must meet all of the following criteria to be eligible for the Registry:

1. Patients electively treated or electively intended to be treated with Edwards PASCAL Transcatheter Valve Repair System.
2. Patient provided written informed consent to participate in the registry.

3.6 Exclusion Criteria

Patients will be excluded from the Registry if they meet the following:

1. Patient is already part of an Edwards Pre or Post Market Clinical study for the PASCAL Transcatheter Valve Repair System.

3.7 Registry Exit Criteria and Procedures

The reason for exit from the registry will be documented on the appropriate case report forms and in the medical records for each patient who exits the registry.

Patients may exit the registry for any of the following reasons:

- Completion per Protocol
- Withdrawal
 - Patient Withdrawal: The patient may voluntarily withdraw from the registry at any time, without penalty or loss of benefits to which they are otherwise entitled.
 - Physician Withdrawal: The Investigator also has the right to withdraw a patient if s/he feels it is in the best interest of the patient to do so.
 - Sponsore Withdrawal: The Sponsor may prematurely terminate the Registry.
- Death
- Device Reintervention or Explant
 - Patients who have a surgical reintervention where the device is explanted will be followed for 30 days post-reintervention or until resolution of any adverse events related to the procedure and then exited from the registry. Patients that have a percutaneous or surgical reintervention where the device remains in place will continue to be followed for the duration of the registry.

- Lost to Follow-up
 - If a patient cannot be reached for a follow-up visit, the Investigator will document the contact efforts made to the patient and/or effort to obtain hospital records in the appropriate electronic case report form. If the patient cannot be reached in any way, or misses a visit, the patient will be considered “unable to contact” for that time interval. After three (3) documented unsuccessful attempts to make contact prove unsuccessful, a certified letter will be sent to the patient’s residence. If there is no response after the certified letter is sent, the patient will be considered “lost to follow-up”.
 - For patients who are lost-to-follow-up or withdraw early, Edwards may request the site to search death registries as available or applicable per GDPR requirements and may request the site to obtain the death certificate, if applicable.

In all cases of withdrawal (as described above), no additional data will be collected.

All data collected up until the time of withdrawal will be analyzed and will be retained for the duration of the registry.

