4.6 Description of Data to Be Collected

Throughout the registry participation, sites will collect patient data per the relevant CRFs in the EDC, as available.

If a patient is followed up in a different location, an effort should be made to obtain copies of source documents from the outside medical facility and kept in the patient's registry file.

Please refer to registry CRF for specific patient level data collected in this registry.

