6 ADVERSE EVENT REPORTING AND ASSESSMENTS

The below described Adverse Events, Interventions and Surgeries will be captured in the eCRF for all registry patients from the time of procedure until the patient's participation has ended (i.e. completion of Registry or withdrawal of consent):

Intra or post procedure events:

Bleed/Vascular: Bleeding at Access Site, Hematoma at Access Site, Retroperitoneal Bleeding, Gastrointestinal Bleed, Gastro Urogenital Bleed, Other Bleed, Transseptal Complication.

Vascular: Major Vascular Complication, Minor Vascular Complication

Additional Procedures: Mitral Valve Re-intervention, Unplanned Other Cardiac Surgery or Intervention (not MVR), Unplanned Vascular Surgery or Intervention (for Bleeding or Access Site Complication), Atrial Septal Defect Closure Due To Transseptal Catheterization

At follow up visits (30 days through annual visits)

Cardiac events: Atrial Fibrillation (new onset), Endocarditis, Myocardial Infarction

Neuro Events: Transient Ischemic Attack, Ischemic Stroke, Hemorrhagic Stroke, Stroke (Undetermined Type)

Device/Delivery System Events: Device Embolization, Single Leaflet Device Attachment, Device Thrombosis, Other Device/Delivery System Related Event

Renal Events: New Requirement for Dialysis

Vascular: Major Vascular Complication, Minor Vascular Complication, Major Bleeding Event, Life Threatening bleeding

Additional Procedures: Mitral Valve Re-intervention, Unplanned Other Cardiac Surgery or Intervention (not MVR), Unplanned Vascular Surgery or Intervention (for Bleeding or Access Site Complication), Atrial Septal Defect Closure Due To Transseptal Catheterization

Readmission: Readmission – Heart Failure, Readmission – Cardiac (not Heart Failure), Readmission – Non-Cardiac

As the registry device is commercially approved, it is the investigator's responsibility to report any complaints as defined in local regulations to the Edwards Complaint Handling Unit To [contact].

Edwards will be responsible for reporting to the National Competent Authority according to national requirements and in line with MEDDEV 2.12-1 (Medical Device Vigilance System).

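### Protocol 3.7 allows a lost-to-follow-up exit after one unreached visit, even the 30-day visit, without a check of routine records in the 10–14 month window, and leaves later data capture unclear.

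*Protocol*

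**What the plan says.** Protocol 3.7 opens its list with "Patients may exit the registry for any of the following reasons" and gives Lost to Follow-up as a reason separate from Withdrawal. The procedure runs in steps:

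- **Trigger.** "If a patient cannot be reached for a follow-up visit, the Investigator will document the contact efforts made to the patient and/or effort to obtain", the last item being records held by hospitals. Any follow-up visit qualifies.
- **Interval status.** "If the patient cannot be reached in any way, or misses a visit, the patient will be considered" unable to contact for that interval.
- **Escalation.** "After three (3) documented unsuccessful attempts to make contact prove unsuccessful, a certified letter will be sent to the patient".
- **Exit.** "If there is no response after the certified letter is sent, the patient will be considered" lost to follow-up.
- **Deaths.** "For patients who are lost-to-follow-up or withdraw early, Edwards may request the site to search death registries as available or applicable per GDPR requirements". Death certificates may also be requested.

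A closing sentence in 3.7 stops further data collection in all cases of withdrawal. It does not name loss to follow-up.

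Protocol 6 captures events, including heart failure readmissions, until the patient's "participation has ended (i.e. completion of Registry or withdrawal of consent". Loss to follow-up is not named there either.

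Protocol 4.4 and 4.5 say that treatment follows standard of care with no added tests, and that clinical and echo data come from clinical records. The 30-day visit may fall up to 2 months after the procedure and the 1-year visit between 10 and 14 months. For patients followed elsewhere, 4.6 adds that "an effort should be made to obtain copies of source documents from the outside medical facility".

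SAP 6.2 analyses endpoints only in patients with the required data. SAP 8.2 reports MR severity at 30 days and 12 months by counts and percentages.

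**The concern.** The exit rule treats an unanswered letter as the end of follow-up. In this registry the data source is the medical record, not contact with the patient. Someone who ignores a letter in the third month may still have a heart failure admission at month 8 or a routine echo at month 12 on file at the site or at another hospital. Neither event needs the patient to reply.

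The protocol does not make the exit wait for the 1-year window, does not require a record check in that window, and does not say whether such records are still entered after the exit. With at least 10 sites, some may close the case and others may continue. The 12-month part of the primary performance measure, late events and 1-year deaths would then be incomplete for reasons that could have been avoided. If patients who cannot be reached early fare differently from the rest, an available-data summary is biased.

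**Working it through.** The documents give no expected loss to follow-up, no event rates and no precision target, so there is no stated figure to reproduce. The main check is of the text. The arithmetic illustrates scale only.

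**1. Can the exit come early?** The trigger is one unreached follow-up visit. The only post-discharge visits in Protocol 4.5 are the 30-day visit (to month 2) and the 1-year visit (months 10–14). The steps carry no minimum duration and no link to the last window. If they finish soon after month 2, the exit precedes the 1-year window by about 10 − 2 = 8 months and its close by about 14 − 2 = 12 months. The timing is inferred, because 3.7 sets no timetable for the attempts or the letter.

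**2. Do records block the exit?** No. Section 3.7 asks the site to document contact efforts and/or efforts to obtain hospital records, but the final status turns on the unanswered letter alone.

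**3. Does capture stop at this exit?** The texts point different ways.

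| Place | Bearing on a lost patient |
|---|---|
| 3.7, reintervention bullet | Sets being exited against continuing to be followed, so an exit suggests that follow-up ends |
| 3.7, closing sentence | Stops data collection for withdrawal; silent on loss, but placed just after the Lost to Follow-up bullet |
| 3.7, death search | Allows some later information, at the sponsor's request |
| 6 | Capture ends at completion or withdrawal of consent; loss not named |
| SAP 5.1.2 | Last participation is the latest date with any information; a lost-to-follow-up exit date is not used |

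No passage settles whether echo and readmission records are entered after the exit.

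**4. Effect on the 12-month MR measure.** Assumptions: N = 200 (the planned minimum), 95% of observed patients at 2+ or less, and 0–20% lost. With n observed and x successes, the available-data rate is x/n with an exact (Clopper–Pearson) 95% interval. Over all 200 patients, the rate lies between x/200 (every lost patient a failure) and (x + 200 − n)/200 (every lost patient a success).

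| Lost | x/n | Exact 95% CI | Bounds over all 200 |
|---|---|---|---|
| 0% | 190/200 | 91.0–97.6% | 95.0% |
| 5% | 180/190 | 90.5–97.4% | 90.0–95.0% |
| 10% | 171/180 | 90.7–97.7% | 85.5–95.5% |
| 20% | 152/160 | 90.4–97.8% | 76.0–96.0% |

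(180/190 is 94.7%, the nearest whole count.) The interval widens only from 6.6 to 7.4 points, while the bounds reach 96.0 − 76.0 = 20 points. The reported interval gives almost no sign of the loss.

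**5. Effect on 1-year mortality.** Assumptions: 12% in patients followed, a share L = 3–10% lost, and mortality d = 20–30% in them, with none of those deaths recovered. Overall mortality = 0.12(1 − L) + dL.

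- L = 0.03, d = 0.20: 0.1164 + 0.0060 = 12.24%.
- L = 0.10, d = 0.30: 0.1080 + 0.0300 = 13.8%.

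The shift from 12% is 0.24 to 1.8 points. For comparison, the exact 95% interval for 24/200 is 7.8–17.3%.

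**The case against.** A reader might infer that 12-month echo, readmission and death data are simply not collected after this exit, or that sections 3.7 and 6 contradict each other. The documents support neither.

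- The only sentence that stops collection is tied to withdrawal, which is a separate exit reason.
- Section 3.7 gives no end of capture for lost patients. Section 6, read alone, favours continued capture, and SAP 5.1.2 is compatible with that. This is an unresolved ambiguity, not a contradiction.
- Deaths have a stated route through registries and certificates, although an optional one.
- One missed visit does not cause an exit. It gives an interval status, and three failed attempts and an unanswered letter must follow.

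These objections stand, and they limit the point. It is also fair that the registry is descriptive with no hypothesis test, that the mortality shift above lies well inside sampling error and rests wholly on assumptions, and that patients entered retrospectively with 12-month records already on file are not at risk. Consent and GDPR terms may restrict record collection on people who do not respond, and the consent form is not among the documents reviewed.

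What the objections do not remove is the rule itself. It permits an exit many months before the 1-year window, with no record check, in a registry built on records. That goes beyond missing detail.

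**Conclusion.** The point holds in a limited form. Section 3.7 allows an exit as lost to follow-up after one unreached visit, including the 30-day visit, once the attempts and the letter have failed. Nothing requires the site to wait for the 10–14 month window or to look for records in it. Whether routine-record echo and readmission data are still entered is unclear, and death ascertainment depends on a sponsor request. It would go too far to say that such data are discarded.

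A patient exited early with no 12-month result leaves the denominator of the 12-month MR measure under SAP 6.2. The size of any bias cannot be derived from the documents. Under the assumed 95% success and 10% loss, the full-cohort rate is uncertain by 95.5 − 85.5 = 10 points beyond what the reported interval conveys as sampling error. These are extreme bounds for loss from any cause, not an estimate of what this rule alone would produce. The change is worth making because the data may be recoverable at little cost, but it does not call the registry's design into question.

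**What to change.** In Protocol 3.7:

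1. Keep the existing interval status for a patient not reached at the 30-day visit, with no exit at that point.
2. Assign the lost-to-follow-up exit only after the 14-month window has closed with no contact and no hospital or outside-facility record in that window.
3. State that, unless consent is withdrawn and subject to the consent and GDPR terms, routine-record data continue to be entered, and that a patient found again is reinstated.

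In Protocol 6, use the same end of capture. The same edit should reconcile the ban on further data after withdrawal with the death search that 3.7 allows for patients who withdraw early.

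Cost: about a paragraph in 3.7 and a phrase in 6, plus a check that the consent form covers continued record collection. Sites keep a few records open for up to a year longer and make one record check at month 14. No visit or test is added.

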4 PROCEDURES AND METHODS

4.1 Site Personnel Training

To ensure uniform data collection and protocol compliance, training is required for relevant registry site personnel in accordance to roles outlined in the Individual Delegation of Authority Log.

Ongoing training may be provided in one of the following formats by the Sponsor or its designee: live training sessions, teleconference, WebEx, online or read and review. Retraining may be performed for sites who have demonstrated protocol compliance issues.

Documentation of site personnel qualifications and training should be maintained in the site’s investigator site file and copies collected and forwarded to the Sponsor.

4.2 Registry Training

An initiation visit for each participating investigation site or, alternatively, a training teleconference shall be conducted and documented by the sponsor or monitor at the beginning of the registry. A log shall be initiated identifying names, initials, signatures, functions, and designated authorizations for the principal investigator and members of the registry site team.

4.3 Informed Consent

The registry investigator(s) and/or delegated registry personnel will approach patients who are candidates for treatment with the PASCAL System to assess their interest in participating in the registry by providing them an overview of the registry. If patients are interested in allowing their data to be used for the registry, the patient will sign the EC-approved informed consent form (ICF) prior to any data being collected.

A patient will be considered enrolled in the registry once the patient has signed the ICF and the procedure has begun (defined as PASCAL guide sheath is inserted into the vasculature).

The Sponsor must approve any modifications to the Informed Consent Form prior to submission to the EC, and/or local regulatory agencies (as required).

Failure to provide informed consent renders the patient ineligible for the registry.

The consent form will be written in the native language of the patient and administered only by the Investigator or EC-approved persons.

The Investigator or delegated person administering the consent must sign and date the ICF to indicate that the purpose of the registry were explained to the patient.

The signed ICF must be retained by the registry site for verification during on-site monitoring visits.

4.4 Patient Treatment

Patients will be treated according to standard of care at their medical facilities and no additional tests or procedures will be performed.

4.5 Data Collected

Routine clinical (such as Medical History, Risk Factors, Medication, Clinical Status, Procedure Information and Safety data) and echocardiographic data available from clinical records will be collected for the following time points:

- Baseline: pre-procedural data
- Procedural data: data collected as part of the procedure
- Discharge data: data collected prior to discharge from hospital
- 30 day visit: visit performed between discharge and up to 2 months post procedure
- 1 year follow up: visit performed between 10 months and 14 months post procedure

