8.3 Secondary Measures

Safety Measures

All AEs and SAEs with onset on or after the procedure date (Day 0) will be summarized using type of event by early events (≤ 30 days) and late events (> 30 days). Summaries of incidence rates (counts and percentages) will be prepared, where data is available.

Functional and Quality of Life Measures

Quality of Life (QoL) as measured by EQ-5D and KCCQ, will be scored according to algorithms provided by the vendor. The various summary scores produced by the algorithms will be analyzed as continuous variables. EQ-5D and KCCQ overall summary scores, and their changes from baseline to 30 days and 12 months will be summarized. Patients that are missing a baseline or follow up values will be excluded from the analysis.

 Edwards	Revision Date: August 22, 2019		Rev	1.0	For Use Only by Affiliates of Edwards Lifesciences	Page 13 of 13
	Title	Statistical Analysis Plan for PASCAL Registry				

Count and percentage of patients in each NYHA Class will be summarized. Change from baseline will be presented as a shift from baseline to 30-day and 12-month follow-up. Patients that are missing baseline or follow-up values will be excluded from the paired analysis.

Summary statistics, including mean, median, SD, and sample size, for 6MWT will be presented. Change in 6MWT at 30 days and 12 months over baseline will be summarized. Patients that are missing baseline or follow-up values will be excluded from the paired analysis. Patients unable to perform the walk due to a medical reason will be considered to have walked a distance of 0 m.

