9. ANALYSIS OF SAFETY

9.1 Deaths

The primary cause of death will be summarized descriptively by counts and percentages at 30 days and 1 year. No statistical testing will be performed.

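### One-year deaths and open-ended late events are tabulated as crude percentages although follow-up can end anywhere from 10 to 14 months and the end of event capture is not fixed

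*Protocol*

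**What the plan says.** Protocol 4.5 (and the synopsis) lists five time points. The last is "1 year follow up: visit performed between 10 months and 14 months post procedure".

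The end of event capture is described in several ways:
- Protocol 6 captures events "from the time of procedure until the patient's participation has ended (i.e. completion of Registry or withdrawal of consent", and no study day is given.
- The same section heads its list of follow-up events "At follow up visits (30 days through annual visits", although 4.5 lists nothing after the 1-year visit.
- Protocol 3.7 gives "Completion per Protocol" as an exit reason without tying it to a visit or a day. It also has patients whose device stays in place after a reintervention followed for as long as the registry lasts.
- On vital status, 3.7 says: "For patients who are lost-to-follow-up or withdraw early, Edwards may request the site to search death registries as available". This is optional, and it does not cover a patient who attended the 1-year visit early.

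On analysis, SAP 9.1 states: "The primary cause of death will be summarized descriptively by counts and percentages at 30 days and 1 year". It does not define 1 year in days or name a denominator. SAP 8.3 splits adverse events "by early events (≤ 30 days) and late events (> 30 days"; the second class has no upper limit, and the statistic is again a count and a percentage. SAP 6.1 provides Kaplan-Meier estimates as a general convention, and SAP 5.1.3 makes the Last Participation Day the censoring day. Neither 8.3 nor 9.1 calls for that method.

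**The concern.** A window of plus or minus two months suits an echocardiogram, a walk test or a questionnaire, each of which describes the patient on the day. A count of events depends on how long the patient was watched. Two patients seen correctly within the window can differ by four months of observation, yet both enter the same crude percentage with equal weight.

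Two things are at stake. First, the late-event percentage depends partly on when sites schedule the last visit. Second, if a patient's participation ends at a visit held before Day 365, a later death within the first year may never reach the database. Deaths after Day 365 can be removed by date at analysis; a death that was not collected cannot be restored. Any such error makes 1-year mortality look lower, in a registry whose stated objective includes safety.

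**Working it through.** The plan states no event rate, precision or 1-year mortality to reproduce, so this is a sizing exercise.

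**Inputs**
- Window of 10 to 14 months (Protocol 4.5). With a month of 365.25/12 days, this is Day 304.4 to Day 426.1.
- N = 200, the planned minimum (Protocol synopsis and 3.3).
- Annual mortality m: 10% and 15% are assumptions. 26.2% and 34% are the background figures in Protocol 1.2 for conservatively treated and for high-surgical-risk patients. None of these is a forecast for this registry.
- No other loss to follow-up.

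**Step 1. Unequal observation after Day 30, counted to the visit**
- Visit at 10 months: 304.4 − 30 = 274 days.
- Day 365: 365 − 30 = 335 days.
- Visit at 14 months: 426.1 − 30 = 396 days.
- Ratio of longest to shortest: 396.1/274.4 = 1.44.

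With an assumed late-event rate r per patient-year, the share of patients with at least one late event is 1 − exp(−r × days/365.25). For r = 0.2 this is 14.0% at 274 days, 16.8% at 335 and 19.5% at 396. For r = 0.1 it runs from 7.2% to 10.3%, and for r = 0.3 from 20.2% to 27.8%. These are extremes, with all visits at one edge of the window.

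**Step 2. Deaths before Day 365 that are missed if capture stops at the visit**

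Constant hazard: h = −ln(1 − m)/365.25 and F(t) = 1 − exp(−h·t).

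Example, m = 26.2%: h = 0.3038/365.25 = 0.000832 per day, so F(304.4) = 22.37% and F(365) = 26.18%.

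- Every visit at 10 months: missed = F(365) − F(304.4).
- Visits uniform over the window: missed = the average of F(365) − F(min(V, 365)), with V uniform on 304.4 to 426.1. About half of the visits fall before Day 365 ((365 − 304.4)/121.75 = 0.50). Those lose on average about half of the full gap, so the result is close to one quarter of the first case.

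| Annual mortality | F(10 months) | F(Day 365) | Missed, all visits at 10 months | Missed, uniform visits |
|---|---|---|---|---|
| 10% | 8.41% | 9.99% | 1.59 points (3.2 per 200) | 0.39 points (0.8 per 200) |
| 15% | 12.67% | 14.99% | 2.32 points (4.6 per 200) | 0.58 points (1.2 per 200) |
| 26.2% | 22.37% | 26.18% | 3.82 points (7.6 per 200) | 0.94 points (1.9 per 200) |
| 34% | 29.27% | 33.98% | 4.71 points (9.4 per 200) | 1.16 points (2.3 per 200) |

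Differences were taken before rounding.

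**Step 3. Comparison with sampling error**

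The 95% half-width at N = 200 is 1.96 × √(m(1 − m)/200): 4.2 points at 10% and 6.1 points at 26.2%. With uniform visits the shortfall is well inside this. Unlike sampling error, it always has the same sign and does not shrink as more patients enroll.

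**The case against.** A reader might infer four stronger things that the documents do not support.

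- **That the 1-year visit completes the registry, so a death at month 11 is certainly lost.** No section says so. This is an inference from the list in Protocol 4.5; 3.7 and 6 leave the end open. The missed deaths are a conditional risk. The openness does not remove the problem, however: if participation continues past the visit, late events accrue over longer and more varied periods, and no visit is scheduled to collect them.
- **That 1-year deaths are counted out to 14 months.** The SAP sets no such cut. Event dates and the Study Day in SAP 5.1.4 allow a cut at Day 365.
- **That the SAP has no method for unequal follow-up.** It has one. SAP 6.2 links Kaplan-Meier censoring to time-dependent endpoints, including secondary measures, and adverse event assessment is one of these. Used at Day 365, it would handle early visits if censoring is non-informative. The gap is that 8.3 and 9.1, which define the tables, name only counts and percentages. Kaplan-Meier also cannot reach Day 365 if nobody is followed that far, so it complements collection of vital status and does not replace it.
- **That 1-year mortality is the central result after 30 days.** It is not a listed outcome measure. The primary performance measure, MR grade at 30 days and 12 months, also provides evidence at that time.

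Two further points stand in part. SAP 9.1 is a cause-of-death table, and its denominator could be the deaths themselves; this is another reason to state it. SAP 8.3 labels late events as occurring after Day 30 and never calls them 1-year rates, so the objection is to mixed exposure in the percentage and not to a false label. Finally, the registry is descriptive, and the typical effect is small beside its sampling error.

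**Conclusion.** The concern holds in a limited form. Followed as written, SAP 8.3 and 9.1 give crude percentages over follow-up that differs up to 1.44-fold among patients seen within the window. The spread could be wider, because SAP 5.2 accepts visits by nominal name even outside the window. The protocol does not say when event capture ends.

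If it ends at the 1-year visit, 1-year mortality may be biased low. With visits spread evenly over the window, the shortfall is about 0.4 points at 10% annual mortality and just under 1 point at 26.2% (about 1 to 2 deaths per 200). It is 1.6 to 3.8 points only if every visit is at 10 months. These sizes rest on a constant hazard, no other loss, assumed or background mortality, and no information reaching the database after the visit.

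The 30-day primary safety measure is unaffected. The effect is modest, but a missed death cannot be recovered at analysis and the remedy is cheap, so the change should be made.

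**What to change.** 1. Keep the 10 to 14 month window for echocardiography, NYHA class, 6MWT and quality of life.
2. Reconcile Protocol 3.7, 4.5 and 6 so that the end of event follow-up is stated once and completion is defined by it. Which of the present wordings reflects the intent is for the sponsor to settle.
3. For patients seen before Day 365, record vital status and the section 6 events through Day 365, from available records or by contact.
4. In SAP 8.3 and 9.1, define 1 year as Day 365. Beside the counts, report Kaplan-Meier estimates at Day 365 for all-cause death and for late events from Day 31 to Day 365. For non-fatal events, cumulative incidence or a rate per patient-year is an acceptable alternative. State the denominator of the cause-of-death table.
5. List events after Day 365 separately, so that none is dropped.

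Cost: a records check or contact for patients seen between 10 and 12 months, short changes to the protocol and SAP, and a little more analysis. No test or extra visit is needed, which respects Protocol 4.4. Contact goes somewhat beyond the use of routine records in 4.5, so records should be tried first. Protocol 3.7 already foresees contacting patients who miss a visit.
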